4.3. ANALYSIS OF THE SECONDARY OUTCOME

The secondary endpoint, twice-daily enoxaparin dose required to achieve target anti-Xa levels, will be summarized with medians and IQRs for all the study participants combined and by age group and MISC status. Distributions will be compared across groups, if there are adequate numbers in the groups, using Mann-Whitney U test.

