# B. **Principal Aims and Hypotheses**

**Specific Aim 1:** To investigate the safety of in-hospital thromboprophylaxis with twicedaily low-dose enoxaparin thromboprophylaxis (starting dose, 0.5 m/gkg subcutaneously q12 hours, adjusted to achieve a 4 hour post-dose anti-factor Xa level of 0.20-0.49 anti-Xa U/mL) in children hospitalized with COVID-19 related-illnesses, as measured by the cumulative incidence of ISTH-defined [10] clinically-relevant bleeding (primary endpoint).

Hypothesis 1: The observed cumulative incidence of ISTH-defined clinicallyrelevant bleeding is ≤2.6% (upper limit of 90% confidence interval: ≤11.8%) among children with COVID-19 who receive in-hospital thromboprophylaxis with twicedaily low-dose enoxaparin.

**Specific Aim 2:** To determine the median twice-daily enoxaparin dose, as measured in mg/kg, required to achieve a 4 hour post-dose anti-factor Xa level of 0.20-0.49 anti-Xa U/mL in children hospitalized with COVID-19 related-illnesses, and to compare dose-requirements by age group (birth to <1 year old, 1-<6 years old, 6-<13 years old, and 13-<18 years old).

Hypothesis 2: Median dose-requirement for anti-Xa-targeted thromboprophylaxis with twice-daily enoxaparin, as measured in mg/kg, in children hospitalized with COVID-19 are associated with age, with younger age groups requiring higher doses.

**Specific Aim 3 (Exploratory):** To investigate, on an exploratory basis, the efficacy of inhospital thromboprophylaxis with twice-daily enoxaparin in children hospitalized with COVID-19, as measured by the proportion of serial D-dimer levels obtained at standardized time points that are <2 times the upper limit of normal (<2x ULN) values for age (Aim 3a; surrogate marker of efficacy), the cumulative incidence of radiologicallyconfirmed HA-VTE (Aim 3b; clinical efficacy), and the median duration of in-hospital increased respiratory support (new requirement for high-flow nasal cannula, non-invasive ventilation, and/or mechanical ventilation, relative to any at-home baseline requirement; Aims 3c, clinical efficacy).

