# H. Data Analysis Plan:

The statistical analysis plan was developed by the lead trial biostatistician. Subject demographics and characteristics at study entry will be summarized with counts and percentages for categorical variables, and with means, standard deviations, medians, and interquartile ranges (IQR) as appropriate, for numeric variables. Missing data will not be imputed. Analysis of the primary endpoint will be conducted on the safety population, which includes all subjects who receive at least one dose of enoxaparin. The primary endpoint, cumulative incidence of ISTH-defined [11] clinically-relevant bleeding events during hospitalization, will be calculated with the corresponding exact (Clopper-Pearson) 90% confidence intervals (90%CIs). The precision of estimates for different cumulative incidences of clinically-relevant bleeds and corresponding 90% Cis are as follows: 0/38, 0% (0-7.6)%; 1/38, 2.6% (0-11.8%); 2/38, 5.3% (0-15.7%). The secondary endpoint, twice-daily enoxaparin dose required to achieve target anti-Xa levels, will be summarized

with medians and IQRs for all the study participants combined and by age group. Medians will be compared across age groups, if there are adequate numbers in the groups, using the Kruskal-Wallis test and a *post-hoc* Bonferroni-adjusted Mann-Whitney U test, if needed. The tertiary endpoints (as outlined in Section IV.B) will be calculated as proportions and cumulative incidences with 90%CIs, and medians with IQRs.

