1. STUDY OBJECTIVES

1.1. SPECIFIC AIM 1

- To investigate the safety of in-hospital thromboprophylaxis with twice-daily low-dose enoxaparin thromboprophylaxis (starting dose, 0.5 m/gkg subcutaneously q12 hours, adjusted to achieve a 4 hour post-dose anti-factor Xa level of 0.20-0.49 anti-Xa U/mL) in children hospitalized with COVID-19 related-illnesses, as measured by the cumulative incidence of ISTH-defined [10] clinically-relevant bleeding (primary endpoint).

1.2. SPECIFIC AIM 2

- To determine the median twice-daily enoxaparin dose, as measured in mg/kg, required to achieve a 4 hour post-dose anti-factor Xa level of 0.20-0.49 anti-Xa U/mL in children hospitalized with COVID-19 related-illnesses, and to compare dose-requirements by age group (birth to <1 year old, 1-<6 years old, 6-<13 years old, and 13-<18 years old).

1.3. SPECIFIC AIM 3

- To investigate, on an exploratory basis, the efficacy of in-hospital thromboprophylaxis with twicedaily enoxaparin in children hospitalized with COVID-19, as measured by the proportion of serial D-dimer levels obtained at standardized time points that are <2 times the upper limit of normal (<2x ULN) values for age (Aim 3a; surrogate marker of efficacy), the cumulative incidence of radiologically-confirmed HA-VTE (Aim 3b; clinical efficacy), and the median duration of in-hospital increased respiratory support (new requirement for high-flow nasal cannula, non-invasive ventilation, and/or mechanical ventilation, relative to any at-home baseline requirement; Aims 3c, clinical efficacy).

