4. STATISTICAL METHODOLOGY

4.1. GENERAL METHODOLOGY

Data analysis for this study will be performed at the JHAC DCC-PMCS at study completion, once the database has been locked and the Statistical Analysis Plan has been finalized and approved by the study team.

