4.1.2. Baseline data

The flow of patients, including the overall eligible patients, excluded patients and patients in the analytic dataset will be presented in a Figure (Figure 1). We will present demographic and clinical characteristics for all patients and by age (<12 and >=12 years) and MISC status (Table 1). Continuous variables will be summarized as means with standard deviations or medians with observed range or interquartile range and compared between groups with independent t-test or Mann-Whitney U test as appropriate. Categorical variables will be summarized as counts with percentages and compared using the Chi-squared test or Fishers exact test as appropriate. All statistical analyses will be performed with SAS v 9.4

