4.2. ANALYSIS OF THE PRIMARY OUTCOME

The primary endpoint, cumulative incidence of ISTH-defined clinically-relevant bleeding events during hospitalization, will be calculated with the corresponding exact (Clopper-Pearson) 90% confidence intervals (90%Cls)

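### SAP 4.3 replaces the protocol's test for the Aim 2 age comparison without giving a reason, and does not say which age grouping it uses

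*SAP*

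**What the plan says.** Both documents state Aim 2 with the same four age groups. SAP 1.2 sets out "to compare dose-requirements by age group (birth to <1 year old, 1-<6 years old, 6-<13 years old, and 13-<18 years old". Hypothesis 2 in Protocol I.B gives the expected direction, "with younger age groups requiring higher doses".

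Protocol IV.H gives a two-step test: "Medians will be compared across age groups, if there are adequate numbers in the groups, using the Kruskal-Wallis test", and then, post hoc, a "Bonferroni-adjusted Mann-Whitney U test, if needed".

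SAP 4.3 summarises dose by age group and by MIS-C status, and gives one sentence on testing: "Distributions will be compared across groups, if there are adequate numbers in the groups, using Mann-Whitney U test". It does not define the age groups. The only other age grouping in the SAP is in 4.1.2, where the baseline table is presented "by age (<12 and >=12 years) and MISC status".

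Neither document states a significance level for Aim 2. The only level stated is that of the interval estimates, for example the "exact (Clopper-Pearson) 90% confidence intervals" of SAP 4.2.

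**The concern.** Mann-Whitney compares two samples. Aim 2 as written has four groups, and the protocol had a matching procedure with control of multiplicity. The SAP keeps the aim, drops both the omnibus test and the adjustment, and does not explain why.

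Two analysts following 4.3 could produce different results. One could run all six pairs of the four groups, each at the nominal level. The other could run a single comparison of children under 12 with those aged 12 or more. The first has an inflated chance of a false age finding. The second does not make the comparison that both documents set as Aim 2. Dose requirement is the only secondary outcome and part of the study's stated purpose, so its test should be unambiguous.

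**Working it through.** **Step 1: the passages side by side.**

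| | Age groups | Test | Adjustment |
|---|---|---|---|
| Protocol I.B and IV.H | Four: cut at 1, 6 and 13 years | Kruskal-Wallis, then Mann-Whitney pairs | Bonferroni |
| SAP 1.2 | The same four | none given | none given |
| SAP 4.1.2 (baseline table) | Two: cut at 12 years | t-test or Mann-Whitney | none |
| SAP 4.3 | Not defined | Mann-Whitney | none |

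The two SAP groupings cannot be reconciled by merging. A child aged 12 belongs to the 6-to-under-13 group of SAP 1.2 but to the older group of 4.1.2, so the cut at 12 divides one of the four groups.

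**Step 2: the four-group reading.** The plan gives no error rate to reproduce. Four groups give 4 × 3 / 2 = 6 pairs. If the six tests were independent, the chance of at least one false positive at 0.05 would be 1 − 0.95^6 = 26.5%. The pairs share children, so this is only an upper guide, and simulation is needed.

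The inputs are N = 38 (SAP 2.5) and no true age difference. Alpha and the group sizes are assumptions: 0.05 as the conventional level, 0.10 to match the 90% intervals, and four possible splits. Under the protocol's method, Kruskal-Wallis must be significant at alpha, and at least one pair must then pass alpha/6 (0.05/6 = 0.0083). There were 10,000 simulated trials per split, with continuous doses and exact Mann-Whitney tests.

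| Split, youngest to oldest | Any of six unadjusted pairs, 0.05 | Same, 0.10 | Protocol's method, 0.05 | Same, 0.10 |
|---|---|---|---|---|
| 9/9/10/10 | 18.2% | 34.6% | 3.0% | 5.7% |
| 5/6/10/17 | 17.9% | 33.2% | 2.9% | 6.3% |
| 4/7/10/17 | 17.7% | 32.2% | 2.3% | 5.5% |
| 3/5/12/18 | 18.8% | 30.8% | 2.0% | 4.9% |

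Repeat runs, some with other splits, gave 16-19% for the unadjusted pairs at 0.05 and about 2-3% for the protocol's method.

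Ties are likely, because Protocol IV.D gives a common starting dose per kg, adjusted in steps. With 50% or 70% of children placed at one dose and tie-corrected tests, the unadjusted pairs gave 14.8-17.7% at 0.05 and 30.6-33.8% at 0.10. The protocol's method gave 0.7-2.1% and 3.1-5.0%. Ties do not change the conclusion.

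**Step 3: the two-group reading.** There is one age test, and Mann-Whitney holds its nominal level (4-5% in a null run at 0.05). There is no inflation within age. What remains is the change of grouping from Aim 2.

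**Step 4: power.** All dose medians and spreads here are assumptions, since the documents give no doses by age. Figures are at alpha 0.05 with log-SD 0.25, for splits 9/9/10/10 and 5/6/10/17, with continuous doses.

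| Assumed pattern | Split at 12 | Kruskal-Wallis alone | Kruskal-Wallis then Bonferroni pairs |
|---|---|---|---|
| Graded 0.70/0.60/0.55/0.50 mg/kg | 50-51% | 53-63% | 41-53% |
| Only infants higher, 0.75 vs 0.50 | 14-20% | 67-91% | 59-87% |
| Only the oldest lower, 0.50 vs 0.60 | 39-49% | 28-37% | 21-27% |

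No method is best throughout. For a steady gradient, the pattern closest to Hypothesis 2, the split at 12 and Kruskal-Wallis are about equal.

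**The case against.** The strongest reply is that 4.3 probably means the split at 12. It pairs age group with MIS-C status just as 4.1.2 does, and 4.1.2 also uses Mann-Whitney for two-group comparisons. Two binary factors and a two-sample test form a coherent plan. This stands as a reading at least as natural as the other. It means that a reader should not take the 16-19% as a property of the SAP: 4.3 never mentions four groups, and the figure applies only if the groups of SAP 1.2 are intended. It does not remove the point, because 4.3 does not say so, SAP 1.2 still states four groups, and the change from the protocol is unexplained.

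A reader might also infer that a test at 12 years says nothing about Aim 2. That goes too far. It bears on Hypothesis 2, that dose falls with age, and for a graded effect its power is similar. It only fails to make the four-group comparison.

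Nor do the documents support inferring that the change was driven by the data. SAP 2.5 reports enrolment in the past tense, so the text was written after enrolment, but nothing shows that doses had been examined. SAP 4.1 places the analysis "once the database has been locked and the Statistical Analysis Plan has been finalized and approved by the study team".

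Finally, the tests depend on adequate group numbers. The protocol carries the same condition, also undefined, so it does not explain the change. It is also true that this is a secondary, largely descriptive outcome in 38 children, which limits the weight of the point.

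**Conclusion.** The point holds as an unexplained departure from the protocol combined with an undefined age grouping. Its size depends on the reading. With four groups, the false-positive rate is about 16-19% at alpha 0.05, or 31-35% at 0.10, against about 2-3% or 5-6% for the protocol's method. With the split at 12, there is no inflation, but Aim 2's grouping has been replaced without acknowledgement. The rates rest on assumed alpha levels and group sizes; across the splits tried, and with heavy ties, they move by only a few percentage points.

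The case for correction rests on fidelity to Aim 2 and the protocol, and on error control if four groups are used. It does not rest on power. The primary safety analysis is unaffected. This should be corrected, but it is at the lower end of that grade.

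**What to change.** In SAP 4.3, state that dose is compared across the four age groups of Section 1.2 by Kruskal-Wallis at a stated alpha. If that is significant, Mann-Whitney tests follow, Bonferroni-adjusted for the number of pairs tested, as in Protocol IV.H. State separately that MIS-C status is compared by Mann-Whitney.

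If the split at 12 is to be used for the dose comparison, say so in 4.3, label it as a change from Aim 2 and the protocol, give the reason, and state whether it was decided before doses were examined.

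Either version can be made when the SAP is finalised and approved. It needs a few sentences and a few lines of SAS, and no new data. The cost of the first version is power. Under the assumed graded pattern at alpha 0.05, the chance that any pair is significant falls from 77-83% unadjusted to 41-53% with the protocol's method (at log-SD 0.35, from 55-63% to 20-27%). If only the oldest group differs, the protocol's method also has less power than the split at 12 (21-27% against 39-49%).

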4.4. ANALYSIS OF THE TERTIARY OUTCOMES

The tertiary outcomes will be calculated as proportions and cumulative incidences with 90%CIs, and medians with IQRs for all the study participants combined and by age group and MISC status

4.5 STUDY POWER

With a sample size of 38 patients in the safety population, the precision of estimates for various cumulative incidences of clinically-relevant bleeding (with corresponding 90% CIs) was as follows: 0/38, 0% (0-7.6%); 1/38, 2.6% (0-11.8%); 2/38, 5.3% (0-15.7%).
